Rationale: Various middle ear diseases can affect anatomical structures of the middle ear in different ways. Unfortunately, current methods for assessing the structure and function of the constituents of the middle ear are limited and often fail to provide all clinically relevant data. Optical coherence tomography (OCT) is a technology that can provide valuable, additional information. Aurisvue is a newly developed prototype OCT-device for structural and functional imaging of the middle ear.

Objective: To assess the feasibility and the clinical potential of structural and functional OCT imaging with Aurisvue in patients with various middle ear problems.

Study design: Observational study

Study population: Adult patients presenting with various middle ear complaints at the ENT-department of the Department of Otorhinolaryngology and Head and Neck Surgery, Erasmus Medical Center, Rotterdam, the Netherlands.

Main study parameters/endpoints: Percentage of patients in which structural OCT imaging was feasible (i.e., the OCT images showed a discernible tympanic membrane (TM) and at least one of the ossicles).

Nature and extent of the burden and risks associated with participation, benefit and group relatedness: The burden is minimal: patient examination with Aurisvue is similar to the conventional examination with a standard otoscope and will take approximately 5 to 10 minutes. The risks are negligible: imaging is done with light levels well below the maximum permissible exposure level and sound levels to induce movement of the TM and the ossicular chain are well below the hazardous threshold.

1. INTRODUCTION AND RATIONALE

The middle ear is an anatomical part of the auditory system that consists of the tympanic membrane (TM), the tympanic cavity and the ossicles. The physical function of the middle ear is to adapt the air-pressure waves to the inner ear's fluid-filled cavity. Acoustic pressure waves are captured by the tympanic membrane and subsequently transferred by the malleus, the incus and the stapes. The footplate of the stapes is located in the oval window, resulting in vibration of the perilymph in the inner ear. The hair cells in the inner ear convert these vibrations into electrical impulses that are transmitted into the central nervous system. The normal middle ear contains air with normobaric pressure.

In patients with otitis media (OM), either acute or chronic, the tympanic cavity is filled with fluid. When this is due to an infection of the upper airway, the patient suffers from acute otitis media. Acute OM is very common, with an incidence rate of almost 11% and more than half of these occurring in children under 5 years old¹. Fluid may accumulate in the middle ear, followed by bacteria and viruses, resulting in the formation of biofilm and in middle ear inflammation. The increased pressure in the middle ear cavity leads to bulging of the TM and may lead to typical symptoms such as pain and fever and common complications are TM rupture and hearing loss (prevalence of 31 per 10.000¹). The chronic type of OM is not a result of a classic bacterial or viral infection, but appears to result from problematic aeration of the tympanic cavity. This can be due to Eustachian tube dysfunction and/or hampered ventilation of the middle ear mucosa. Treatment options of OM include observation, medication to reduce the symptoms, antibiotic therapy or surgical placement of tympanostomy tubes².

A special type of OM is cholesteatoma. In this condition, the skin of the tympanic membrane grows into the middle ear cavity and the mastoid leading to erosion and finally destruction of bony structures including the ossicles and the mastoid, the facial nerve and the semicircular canals (vestibular system). Patients usually suffer from a chronically discharging ear, hearing loss and sometimes vertigo.

Hearing loss related to the middle ear can be due to perforation or retraction of the tympanic membrane, middle ear effusion, erosion or dislocation of the ossicles and ankylosis of the stapes (otosclerosis). All these conditions can cause a conductive hearing loss. To determine the cause of this type of hearing loss, otoscopy is the first diagnostic procedure. This is performed with a hand-held otoscope or with a binocular microscope. Because the tympanic cavity is sealed by the TM which is partially transparent, visualization of the middle ear structures is not as straightforward. Computed tomography (CT) and magnetic resonance imaging (MRI) are the most common imaging modalities for imaging middle ear pathology³. High-resolution CT scanning can be used to visualize the middle ear including the ossicles

and the inner ear, but very small structures like the stapes arch can be difficult to identify. Differentiation of cholesteatoma from other types of tissue and from fluid is difficult with CT. Moreover, CT involves radiation exposure. MRI is used in special cases when soft tissue structures need to be visualized. These are the internal auditory canal, fluid in the cochlea and labyrinth and cholesteatoma. Currently, there is no functional imaging modality available to identify the location of reduced transduction of vibration in case of conductive hearing loss. Therefore, the ossicular chain is often best inspected during surgery. The availability of an imaging technology that is able to identify middle ear structures in high resolution and assess the transduction of acoustic vibrations by the ossicular chain, might reduce the burden on the patient, provide additional insight to the clinician to more accurately diagnose the cause of conductive hearing loss, improve surgical planning and evaluate the result of a reconstructive procedure.

Optical coherence tomography (OCT) is an interferometric imaging modality that produces depth-resolved images of semi-transparent media⁴. It was first developed for ophthalmology and is routinely used in clinical practice for over a decade. It enables volumetric, high-resolution imaging of, for example, the chorioretinal complex, where many different layers can be visualized. Similar to ultrasound, Doppler-OCT, an extension to OCT, can also be used to measure motion, e.g., blood flow⁵. Due to the semi-transparent nature of the TM, OCT may also be used for imaging of the middle ear to identify the TM, any fluid behind the TM and the ossicular chain (see Figure 1). Doppler-OCT can be used to measure the vibrations of the various components of the auditory system (i.e., the TM and the ossicles; OCT-vibrometry, see Figure 2)⁶.

[figure not shown]

Figure 1. In vivo OCT imaging of a normal subject's left ear. A) Shows a $1 \times 1 \text{ cm}^2$ 2D cross-section of the middle ear in the transverse plane. B) Shows a $1 \times 1 \times 1 \text{ cm}^3$ 3D volume render of the middle ear as seen from the perspective of the ear canal with the TM digitally removed. Tympanic membrane (TM), malleus (M), incus (IN), incudo-stapedial joint (IS), stapedius tendon (ST), chorda tympani nerve (CT), cochlear promontory (CP), round-window niche (RW).⁷

[figure not shown]

Figure 2. (a)-(b) Overlay of vibratory response (color scale) on the morphological image (gray scale) of the middle ear. (a) Pure tone stimulus was at 800 Hz and 70 dB SPL. (b) Bone stimulus calibrated to give similar vibratory response at the cochlear promontory. (c) Morphological image showing the 3 regions of interest (ROI) used to generate the plots in (d) and (e). (d) Plot of the displacement for the ROI at the TM and bone (Cochlear Promontory or Incus) resulting from air and bone stimulation. (e) Displacement data from (d) plotted relative to the vibratory response at the cochlear promontory.⁸

Preliminary results from many different prototype research instruments have been published, primarily focused on imaging of the TM and any adjacent fluid, although other diseases were also explored⁹⁻¹². Despite the heterogeneous set of devices, methodologies and diseases, the results indicate that application of OCT in otology is promising and could provide clinically relevant information that is currently not available.

To the best of our knowledge, no systems have been approved in the EU for clinical use in otology. Aurisvue CIM is a novel, handheld, clinical prototype OCT device, developed by Acoustic Insight. It features both structural OCT imaging and functional OCT imaging (OCT-vibrometry) and is specifically designed for middle ear imaging. In this study, we aim to identify clinically relevant applications of Aurisvue for middle ear imaging. Based on the results from this study, Aurisvue will be further developed for specific clinical applications and evaluated in future trials.

2. OBJECTIVES

Primary Objective:

- To assess the feasibility of structural OCT imaging with Aurisvue in clinically relevant subjects with middle ear problems.

Secondary Objectives:

- To assess the feasibility of functional OCT imaging with Aurisvue in clinically relevant subjects with middle ear problems.
- To assess the clinical potential of structural and functional OCT imaging with Aurisvue in clinically relevant subjects with middle ear problems.

3. STUDY DESIGN

This study is an observational study. No treatment intervention for study purposes is included and all patients will receive routine clinical care. The study is intended to explore the feasibility and possibilities of OCT for structural and functional imaging of the middle ear.

The duration of the study will be approximately one year. Patients will be recruited from those visiting the Department of Otorhinolaryngology and Head and Neck Surgery, Erasmus Medical Center, Rotterdam, the Netherlands.

Patients included in the study will be imaged at least once with Aurisvue. If a patient returns to the site within the duration of the study and relevant physiological or pathological changes to the middle ear are expected (due to, for example, treatment or the natural history of the disease), the patient may be imaged again. Except for assessment with Aurisvue, no study related procedures are prescribed, and patients will receive the usual standard of care.

4. STUDY POPULATION

4.1 Population (base)

Approximately 100 patients will be recruited from those visiting the ENT-department with various middle ear problems, as assessed by the otolaryngologist. Because a heterogenous study population is needed to evaluate a wide range of abnormalities of the middle ear, patients will be stratified according to the table below.

condition	Max. number of patients
chronic suppurative otitis media	10
conductive hearing loss of unknown origin	20
conductive hearing loss after head trauma	10
cholesteatoma	10
perforated tympanic membrane	10
total middle ear prosthesis TORP in situ	10
partial middle ear prosthesis PORP in situ	10
interpositioned incus in situ	10
cochlear implant in situ	10
previous tympanoplasty	10
glomus tumor in middle ear (glomus tympanicum)	10
sclerosis of the tympanic membrane (myringosclerosis)	10

4.2 Inclusion criteria

In order to be eligible to participate in this study, a patient must meet all of the following criteria:

- age 18 or older,
- competent, willing and able to cooperate.

4.3 Exclusion criteria

A potential subject who meets any of the following criteria will be excluded from participation in this study in case of:

- any acute or chronic condition that would limit the ability of the patient to participate in the study, per attending physician's indication, including:
 - o abnormally narrow or stenotic external ear canal,

- external otitis,
 - significant exostosis of the ear canal,
 - radical cavity,
 - movement disorder causing inability to keep head still during imaging.
- refusal to give informed consent
 - pregnancy or breastfeeding

4.4 Sample size calculation

Due to the exploratory nature of this study, no formal sample size calculation can be performed. The study aims to include patients with various middle ear problems (disease). For each specific disease, not more than the specified maximum number of patients will be included. The total number of included patient will not exceed 100.

5. TREATMENT OF SUBJECTS

Not applicable as this is not an intervention study.

6. INVESTIGATIONAL PRODUCT

6.1 Name and description of investigational product(s)

Product name: Aurisvue CIM

Aurisvue is an optical coherence tomography (OCT) system designed specifically for assessing the structure and function of the middle ear.

For further details, please refer to chapter 1 (section 2.1) of the IMDD.

6.2 Summary of findings from non-clinical studies

Not applicable because sufficient data is available from clinical studies to assess the basic safety and potential applicability of the technology.

6.3 Summary of findings from clinical studies

Please refer to chapter 6, section 2 of the IMDD.

6.4 Summary of known and potential risks and benefits

Please refer to chapter 5 of the IMDD.

6.5 Description and justification of route of administration and dosage

Not applicable.

6.6 Dosages, dosage modifications and method of administration

Not applicable.

6.7 Preparation and labelling of Investigational Medicinal Product

Not applicable.

6.8 Drug accountability

Not applicable.

7. NON-INVESTIGATIONAL PRODUCT

Not applicable, the study does not concern any non-investigational products.

8. METHODS

8.1 Study parameters/endpoints

8.1.1 Main study parameter/endpoint

Presence of a discernible TM and the number of discernible ossicles on structural OCT imaging.

8.1.2 Secondary study parameters/endpoints (if applicable)

- Number of middle ear structures (TM, ossicles) on which OCT-vibrometry measurements by Aurisvue succeeded.
- For diagnostic correlation with other clinical data sources (only as far as they are available from the standard of care):
 - o microscopic otoscopy (description)
 - o CT-scan
 - o MRI-scan
 - o pure-tone audiogram
 - o tympanogram
 - o surgical report (if available)
- Number of AEs and SAEs
- PREMs

8.1.3 Other study parameters (if applicable)

- Demographic characteristics
- Clinical diagnosis of middle ear disease
- Description of relevant interventions before or during study period (if applicable)

8.2 Randomisation, blinding and treatment allocation

Not applicable.

8.3 Study procedures

Discernible TM and discernible ossicles on structural OCT imaging.

OCT images acquisition by Aurisvue will be performed on both ears of every patient. The acquisition process consists of positioning the Aurisvue's handheld interface in the ear canal of the patient and collecting data during a period of a few minutes. Several two- or three-dimensional scans may be acquired during this time, each focusing on regions of interest in the middle ear. During acquisition, the OCT images are displayed on the monitor of the

computer to guide the operator. Data may be processed at a later stage to improve image quality. The processed images will be evaluated by a medical specialist to identify the anatomic features. Visibility of the TM and of the ossicles will be registered as outcomes (primary endpoint).

Number of middle ear structures (TM, ossicles) on which OCT-vibrometry measurements by Aurisvue succeeded.

The assessment procedure for OCT-vibrometry is similar to the structural imaging described above. In OCT-vibrometry mode, Aurisvue will produce a sound stimulus and will subsequently measure differences between repeated scans. Vibrometry is successful if the signal on the region of interest is sufficient to determine the amplitude of the vibration that matches the characteristics of the stimulus.

Diagnostic correlation with other clinical data sources from the standard of care.

Procedures/assessments may include:

- microscopic otoscopy (description)
- CT scan
- MRI scan
- pure-tone audiogram
- tympanogram
- surgical report (if available)

These procedures/assessments will all follow the standard of care at the clinical site. Both the results of the assessments and the interpretation thereof by the clinician will be used to evaluate the diagnostic correlation with structural and functional imaging results by Aurisvue.

PREMs (for subjects).

Patients will be asked about their experience with otoscopy with Aurisvue compared to regular or microscopic otoscopy (one question).

Number of AEs and SAEs

These will be reported as detailed in section 9 (Safety reporting).

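### Nothing requires the OCT reading to be completed before the reader sees the clinical findings it is later compared with

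*Combined protocol and SAP*

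**What the plan says.** Section 8.3 describes the reading in one sentence: "The processed images will be evaluated by a medical specialist to identify the anatomic features". The result is the main endpoint, given in section 8.1.1 as "Presence of a discernible TM and the number of discernible ossicles on structural OCT imaging". The Summary expresses it as the percentage of patients in whom "the OCT images showed a discernible tympanic membrane (TM) and at least one of the ossicles". The plan does not say whether the specialist operates the device, treats the patient or belongs to the site team, or what other information the specialist may have at hand. It sets no time for the reading, and 8.3 allows the images to be processed after the visit.

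Section 8.2, headed "Randomisation, blinding and treatment allocation", has a single entry for all three topics: not applicable.

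Sections 8.1.2 and 8.3 list the comparison sources, as far as routine care provides them: microscopic otoscopy, CT, MRI, pure-tone audiogram, tympanogram and surgical report. Section 8.3 adds that "Both the results of the assessments and the interpretation thereof by the clinician will be used to evaluate the diagnostic correlation" with the Aurisvue results. Section 10.2 makes this comparison qualitative and looks at both agreement and disagreement, including features that OCT shows and another modality does not. Section 8.1.3 also collects "Clinical diagnosis of middle ear disease" and "Description of relevant interventions before or during study period".

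**The concern.** Whether a structure is discernible is a subjective call. A specialist who has read the CT or surgical report may recognise an ossicle partly because it is known to be there, or dismiss an ambiguous signal because it is known to be absent. If the OCT reading is shaped in this way by a source with which it is then compared, agreement is partly circular. Disagreement is affected too, because a reader who knows what CT showed may look differently for what it did not show.

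The second secondary objective, clinical potential, has most at stake. The Introduction argues that OCT may supply information that current methods lack, and says that the results will guide further development for specific applications and evaluation in future trials. The 10.2 comparison bears on that argument only as far as the OCT reading was made independently of the other sources. If neither the order of reading nor the reader's knowledge is recorded, the influence of that knowledge cannot be separated out afterwards.

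**Working it through.** The documents give no alpha, power, effect size or calculated sample size on this point, so there is no figure to reproduce. The check sets the relevant sections side by side.

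1. **Who reads, and by what standard.** Section 8.3 names one unspecified medical specialist. The Summary defines feasible imaging as the TM plus at least one ossicle, but no section defines discernible. The reading is therefore a judgement that prior knowledge can influence.

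2. **What is known before imaging.** Under section 11.2 patients are screened from medical records or referral information. Under section 4.1 they are recruited by condition. The condition is thus known at the site before imaging. Whether the reader is part of the site team is not stated.

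3. **Whether pseudonymisation hides it.** Section 12.1 places images and all other data in one electronic data capture (EDC) system under the study code. The investigator and the site's study team hold the key. Reading by code therefore does not by itself keep the other findings from the reader.

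4. **Whether any order is set.** Section 8.2 supplies no rule for the reader. Sections 8.3, 10.1 and 10.2 do not say that the OCT result is recorded before the comparison sources are opened. Steps 1 to 4 together mean that a site can follow the plan exactly and still read the OCT images with the CT or surgical report in view.

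5. **What in 10.2 is exposed.** The comparison uses the data obtained by Aurisvue generally. That covers TM and ossicle visibility, vibrometry results and other image characteristics. A rule that covered visibility alone would leave the rest of the comparison unprotected.

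6. **Which part of the primary endpoint is more exposed.** Take one ear with a discernible TM. The Introduction names three ossicles (malleus, incus, stapes), so the count runs from 0 to 3 and one changed ossicle call moves it by one step:
   - 0 to 1: the count changes, and so does the Summary classification.
   - 1 to 2: the count changes, the classification does not.
   - 2 to 3: the count changes, the classification does not.

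   All 3 steps alter the count in 8.1.1, and 1 of the 3 alters the classification behind the percentage. The steps need not be equally likely, and the documents give no frequencies. This ranks the two measures by exposure and does not estimate a bias.

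7. **Where withholding information could do harm.** Section 4.1 allows at most 10 patients each with a TORP, a PORP and an interpositioned incus: 10 + 10 + 10 = 30. In these ears a reader unaware of the surgery could count a prosthesis or repositioned incus as a native ossicle.

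**The case against.** The strongest case on the other side has four parts.

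- **The study is exploratory and single-group.** Section 4.4 has no sample size calculation, 10.1 is descriptive, 10.2 is qualitative and 10.3 rules out definite conclusions from stratified results. This stands. It limits the consequence to interpretation, but does not make a comparison with already known findings independent.

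- **The primary endpoint has no reference standard.** It asks only whether structures can be discerned, so circularity cannot arise there. This also stands. What remains for the primary endpoint is a possible expectation effect on a descriptive result.

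- **Reading with clinical context is a legitimate choice in a feasibility study.** It may be, but the plan does not state that choice. A shared not-applicable entry neither describes nor justifies what the reader may know.

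- **Full masking could create error.** This stands for ears with a prosthesis or interposed incus, and is a reason not to withhold that fact.

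A reader might infer that the feasibility percentage is overstated, or that the treating clinician does the reading. The documents support neither: they give no basis for the direction of an effect and do not identify the reader. Nor can the effect be sized by multiplying patients, ears and structures, since that would count readings without a rule rather than measure bias.

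**Conclusion.** The gap is real and narrow. The plan permits the OCT reading to be made with knowledge of the sources it is compared with, so the similarities and dissimilarities in 10.2 can be partly a product of that knowledge. For the primary endpoint an expectation effect is possible, mainly on the ossicle count and less on the Summary percentage. Its size and sign are unknown. There is no test or success threshold in the analysis, so type I error and power are untouched.

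This rests on two assumptions: that judging discernibility can be influenced by prior knowledge, and that at least some comparison sources are available when the images are read. The second will vary by patient, since 8.1.2 uses only what routine care provides. The change is a cheap improvement that makes the 10.2 results easier to interpret. The gap does not invalidate the study.

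**What to change.** In sections 8.2, 8.3 and 10.2, state that the specialist records and locks the following by study code before opening that patient's otoscopy, CT, MRI, audiogram, tympanogram or surgical report for the study:

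- (a) TM and ossicle visibility;
- (b) vibrometry success for each structure;
- (c) the OCT image characteristics to be compared under 10.2.

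The comparison then follows as a second step. The reader may be told whether a prosthesis, interposed incus or implant is in situ, so that it is not counted as a native ossicle. For each reading, record whether the reader operated the device, treated the patient, or already knew the diagnosis or the comparator findings. Report this with the results as a limitation.

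The cost is protocol wording, data fields for the locked items and for prior knowledge, and an order rule. Section 12.1 does not say whether the EDC system can enforce an order of entry; if it cannot, a dated score form completed first would serve. No extra reader and no extra patient procedure are needed. Reading becomes a separate step or is done in batches, which fits the later processing that 8.3 already allows. Masking will be incomplete where the reader knows the patient or the image itself shows the condition, which is why prior knowledge should be recorded.

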10.2 Secondary study parameter(s)

Answering the first secondary objective ('To assess the feasibility of functional OCT imaging with Aurisvue in clinically relevant subjects with middle ear problems') will be done in the same way as described above for the primary objective, albeit based on functional OCT-vibrometry measurements using a sound stimulus rather than the structural OCT images.

For the second secondary objective ('To assess the clinical potential of structural and functional OCT imaging with Aurisvue in clinically relevant subjects with middle ear problems'), the data obtained by Aurisvue will be (qualitatively) correlated with other clinical data sources. Similarities (such as Aurisvue image information consistent with other imaging modalities) and dissimilarities (such as characteristics visible on Aurisvue images but not on another imaging modality) will be evaluated.

AEs, SAEs and questionnaires will be included in answering the primary and both secondary objectives. Again, missing data will be reported and not imputed.

Patient reported experience measures (PREMs) will be recorded immediately after the measurements with Aurisvue are completed.

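### For comparators written after the Aurisvue scan, nothing keeps the OCT result from their author or separates those pairs in the analysis, so similarities may be overstated and OCT-only findings masked

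*Combined protocol and SAP*

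**What the plan says.** The second secondary objective is the clinical potential of structural and functional OCT imaging. Section 10.2 addresses it by a qualitative comparison of Aurisvue data with other clinical sources, looking at both similarities and dissimilarities. Its example of a dissimilarity is a feature that Aurisvue shows and another modality does not.

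Sections 8.1.2 and 8.3 list the sources: the microscopic otoscopy description, CT, MRI, pure-tone audiogram, tympanogram and, where there is one, the surgical report. Section 8.1.2 takes them "only as far as they are available from the standard of care". Section 8.3 adds: "Both the results of the assessments and the interpretation thereof by the clinician will be used to evaluate the diagnostic correlation".

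On the OCT side, section 8.3 says that during acquisition "the OCT images are displayed on the monitor", to guide the operator. Afterwards, "The processed images will be evaluated by a medical specialist to identify the anatomic features". Neither the operator nor the specialist is described further.

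On masking, the whole of section 8.2 is: "8.2 Randomisation, blinding and treatment allocation Not applicable". Section 3 says that "all patients will receive routine clinical care", and it foresees treatment and repeat imaging while the study runs. Section 8.1.3 records relevant interventions before or during the study period.

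**The concern.** A comparator tests the device only if it was formed without knowledge of the device's result. Here it includes descriptions and interpretations written by clinicians, some of which can be written after the scan. A surgeon or radiologist who knows what OCT suggested may look for that finding and describe it. The record is then counted as a similarity although it is not independent. This concerns what the author of the comparator knows; masking the OCT reader would not remove it.

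The effect on the objective can go two ways. Agreement may look better than it is, with OCT errors under-reported. A feature first seen on OCT may also be absorbed into the later clinical record, so that it no longer appears as something only OCT showed. Section 10.2 treats that kind of dissimilarity as informative. Section 1 says the results will guide further development of the device and future trials, so a distorted picture would carry forward.

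**Working it through.** The plan states no agreement figure, power or error rate for this comparison, so there is nothing to reproduce. The check is mainly of the text, followed by an illustration.

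**1. Does any section close the route?**

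- Section 8.2 has no masking provision. That is natural where no treatment is allocated, but it leaves the diagnostic comparison without a rule.
- Section 8.3 does not require the OCT reader to differ from the treating clinician, and does not withhold the reading from later authors.
- Section 3 promises usual care. It does not say that OCT findings stay unknown to those giving it.
- Section 12.1 limits access to the study team and authorities. It is a privacy rule and does not place the treating clinician or surgeon outside the team.
- Section 10.2 does not classify pairs by timing or by the author's knowledge.

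So the route is open where a comparator follows the scan, and the planned analysis would not show which pairs are concerned.

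**2. Which comparators are exposed?**

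| Comparator | Exposure |
|---|---|
| Any record finalised before the scan | None |
| Audiogram and tympanogram values | Small; they depend little on interpretation |
| Otoscopy description, CT or MRI reading made after the scan | Possible |
| Surgical report written after the scan | Possible; section 1 says surgery is often the best way to inspect the ossicular chain |

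Under section 11.2 the research visit is arranged by telephone at least 2 days after the clinic visit. Some comparators will therefore already exist when the scan is made.

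The table in section 4.1 has eleven conditions with a maximum of 10 and one with 20: 11 × 10 + 20 = 130 places. Five conditions imply earlier surgery (TORP, PORP, interpositioned incus, cochlear implant, previous tympanoplasty): 5 × 10 = 50 places. The other 130 − 50 = 80 do not. Section 4.4 caps enrolment at 100. If 100 are enrolled, between 100 − 80 = 20 and 50 patients fall in the earlier-surgery strata. Their index operation precedes the scan; a further operation during the study remains possible.

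**3. Illustration of size (all inputs assumed)**

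Let a be agreement with an independent comparator, s the share of comparators written after the scan by an author who knows the OCT result, and f the share of would-be disagreements that then resolve toward OCT.

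Observed agreement = a + s × f × (1 − a)

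With a = 0.70:

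| s | f | Calculation | Observed | Shift (points) |
|---|---|---|---|---|
| 0 | any | 0.70 + 0 | 0.700 | 0 |
| 0.25 | 0.10 | 0.70 + 0.025 × 0.30 | 0.7075 | +0.75 |
| 0.50 | 0.25 | 0.70 + 0.125 × 0.30 | 0.7375 | +3.75 |
| 0.50 | 0.50 | 0.70 + 0.25 × 0.30 | 0.775 | +7.5 |
| 1 | 0.50 | 0.70 + 0.50 × 0.30 | 0.850 | +15 |

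Over a from 0.60 to 0.80, s from 0 to 1 and f from 0.10 to 0.50, the shift runs from 0 to +20 points. The maximum is at a = 0.60: 0.60 + 0.50 × 0.40 = 0.80. The shift cannot be negative because the model only moves disagreements toward OCT; that is an assumption, not a finding. The value s = 1 describes a set made up entirely of post-scan records by aware authors, so it is an upper limit for the study as a whole.

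**The case against.** The strongest case against is that the exposure is inferred. The live display serves the operator, who is not identified as the treating clinician. Images go into the study database under a code unrelated to the clinical patient number, with restricted access (section 12.1). Many comparators predate the scan. The comparison is qualitative with no agreement statistic, it serves one secondary objective, and section 10.3 disclaims definite conclusions. Surgery is also direct inspection, so a report may not bend easily toward a prior image.

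Most of this stands, and it limits the point to post-scan comparators and to a possible effect. It does not remove the point. Restricted access helps only if the author of the comparator is outside the study team, which is not stated. A qualitative account of similarities is also hard to interpret if the non-independent ones cannot be picked out, and authors' awareness cannot be reliably reconstructed later.

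A reader might infer more: that treating clinicians do see the OCT, that the OCT reader works in the treating department, that the case report form has no field for awareness, or that agreement is inflated. The documents support none of these. They do not say that results reach the clinician, they name no department for the reader, and the case report form is not among them.

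**Conclusion.** The point holds for comparators produced after the scan. For those pairs the plan has no safeguard and no separate presentation, so similarities may be overstated and OCT-only findings may be masked. Comparators finalised before the scan are not affected, audiogram and tympanogram values are largely not affected, and the primary feasibility endpoint is untouched.

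How many pairs are involved is unknown, because the documents give neither the number of post-scan comparators nor how often their authors would know the OCT result. At an assumed 70% independent agreement, the shift is 0 when authors are unaware and about +15 points in the most exposed case considered. These figures show what is possible; they do not estimate what will happen. The point does not invalidate the study. It is a low-cost improvement that would let the second secondary objective distinguish independent from non-independent similarities.

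**What to change.** In section 8.3, record two items for each comparator: its date relative to the Aurisvue scan, and whether its author had seen the Aurisvue result (yes, no or unknown).

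In section 10.2, present similarities and dissimilarities in two groups. The first holds independent pairs, where the comparator was finalised before the scan or its author was unaware of the result. The second holds all remaining pairs, including those with awareness unknown. State that the conclusion on clinical potential rests primarily on the first group, and that no pair is discarded.

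The cost is two data items per comparator and a few sentences of text; patient care does not change. The drawback is a smaller independent group. It may lose some post-scan surgical reports, which are among the most informative comparators for the ossicles; keeping them visible in the second group limits that loss.
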